5.2. STUDY PROCEDURES AT EACH VISIT

All visits should be done in the morning at the same time to ensure identical evaluation conditions along the study, if possible.

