5.2.7. V6 – Control treatment visit (Day 49 ± 2 days)

A complete interrogation including occurred of possible adverse events and concomitant

medication used will be done and recorded,

A physical examination including vital signs shall be carried out,

12-lead ECG recording with calculation and control of QTcF,

The following questionnaires should be performed:

- PDSS,

- CASS,

- CDI,

- C-SSRS,

- UNS,

- TEA-Ch,

- Clinical Global Impression of Change (CGI-C) on EDS and on cataplexy,

- Retrieval of sleep diary of the previous visit and check by the investigator. Delivery of one

other sleep diary which have to be completed every evening until the next visit.

No dispensation performed at V6.

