5.2.8. V7 – End of Double Blind period (Day 56 ± 2 days)

This visit should be **imperatively** done in the morning (around **9.30 a.m.**) and all further visits

should be done at the same time of day, if possible, to ensure identical evaluation conditions

along the study.

Patients will be required to have sufficient nocturnal sleep (minimum 6 hours) and not

drink alcohol during the night prior to this visit. An optional polysomnography can be done in

accordance with the processes of sites, the evening preceding the MWT test to confirm a sufficient

nocturnal sleep. The patient will be required to take a light breakfast before 8.00 a.m. and arrive

at the trial center around 9.00 a.m. They should refrain from drinking any stimulatory beverage

such as coffee, tea or Coca-Cola this morning until the end of this visit.

The first session of MWT will approximately start at 10.00 a.m.

A complete interrogation including occurred of possible adverse events and concomitant

medication used will be done and recorded,

A physical examination including vital signs shall be carried out,

12-lead ECG recording with calculation and control of QTcF,

A blood sample will be taken for routine haematological and biochemical test (including β-

HCG pregnancy test for pubescent female) and semi-quantitative urinalysis (dipstick),

A urine drug testing (for patients from 12 years),

The following questionnaires should be performed:

- PDSS,

- CASS,

- C-SSRS,

- UNS,

- CGI-C on EDS and on cataplexy,

EudraCT number: 2013-001506-29

- Retrieval of sleep diary of the previous visit and check by the investigator. Delivery of one

other sleep diary which have to be completed every evening until the next visit,

-Patient's Global Opinion on the effect of investigational treatment if able to express himself.

If not will be reported either by parents or teachers.

Investigational treatment allocation: start 1-week wash-out period.

The treatment pack bring back from previous visit by patient is checked by investigator for the

compliance.

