## Maintenance of Wakefulness Test 30-minute version

For this assessment the four test have been considered. Therefore, arithmetic means and sum on these 4 tests are computed.

**Mean value for each latency parameter**, in minutes, for a visit, will be estimated as the arithmetic mean of the 4 tests.

**Before this mean computation each latency parameter** (sleep onset, Stade I, Stade II, stade III and SP) must be recalculed to take into account the "Awake" status and the test duration:

- For a test, if "Awake"= "yes" then the sleep onset latency has to be considered at 30min (even if another value is entered).

- If a reported value is greater than 30min this value will be censured at 30min.

Number of Sleep onset in SP for a visit, will be computed as the sum of Yes (=1) of the 4 tests.

A survival response will be computed according to the "sleep onset latency" recalculed:

- Non-response (0=patient remained awake until 30 minutes) = Mean sleep onset latency ≥ 30min.
- Response (1=patient falling asleep before 30 minutes) = Mean sleep onset latency < 30min.

- Patient sleep diary
- Rate of cataplexy (WRC), Number of diurnal involuntary sleep attacks and episodes of severe daytime sleepiness (NSAE) and Number of hallucinations and sleep paralysis episodes (NHS) are weekly ratio computed as :

[Number of episodes of the concerned parameter in the period / Number of days in the period] \* 7

Whith Number of days in the period= Date of the last visit of the period - Date of the first visit of the period + 1

Results are rounded to to the nearest integer number.

- Night duration (NightD), in hours, is calculated as:

Wake-time (morning) - Hour of bedtime (evening)

The mean of night duration per day during the studied period is computed as:

Sum of night duration in the period / Number of days in the period

Whith Number of days in the period= Date of the last visit of the period - Date of the first visit of the period + 1

The result is rounded to one decimal place.

In case of several hours at the same date the following rule will be applied:

- For wake-time the last hour will be kept
- For bedtime the first hour will be kept

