#### Analysis:

Descriptive statistics by treatment group during the following intervals: Baseline (D-28 to D0), Final DB last 6 weeks DB4=D21-D63, Final DB last 2 weeks: DB2=D49-D63 will be provided

Missing data handling:

Missing evaluations are not imputated

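### Mean night duration divides k nights by k + 1 calendar days, so a complete diary understates hours slept by an amount that depends on window length (2.3% to 6.7% on the planned windows)

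*SAP*

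**What the plan says.** SAP 4.1.5.5, under the patient sleep diary, computes one duration per night as the morning wake-time minus the evening bedtime. The mean for a period is "Sum of night duration in the period / Number of days in the period", and the number of days is "Date of the last visit of the period - Date of the first visit of the period + 1". On precision it adds: "The result is rounded to one decimal place".

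SAP 4.5.3.3.6 describes night duration by treatment group over three intervals: baseline D-28 to D0, the last six weeks (DB4, D21–D63) and the last two weeks (DB2, D49–D63). Missing evaluations are not imputed. SAP 4.5.3.2.3 uses the same DB4 and DB2 labels and dates for the cataplexy rate, but there equates them with V4–V7 and V6–V7. V7 is D56, not D63.

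Protocol 5.2 says: "All visits should be done in the morning at the same time". Each diary is filled in every evening until the next visit (Protocol 5.2.4 to 5.2.8). Patients on no prohibited or anticataplectic medication may start at V1 (D-14) instead of V0 (D-28), according to note 8 of the visit schedule.

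**The concern.** The numerator counts nights and the denominator counts calendar dates, including both visit dates. Between two mornings there is one night fewer than there are dates. The divisor is therefore one too large even when the diary is perfect, and the proportional error grows as the window shortens. The planned windows differ in length, and baseline itself differs between patients starting at V0 and at V1, so the error does not cancel when one column of the table is compared with another.

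The same divisor has a second effect. A night with no entry adds nothing to the sum but stays in the day count, so it is treated as a night of zero hours.

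At stake are the absolute hours reported and any movement between baseline and treatment windows that a reader takes from the table. Insomnia is among the more common adverse events listed in Protocol 1.3 (9.3%), so a reader may look at this table for sleep loss.

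**Working it through.** The plan states no numerical result for night duration, so there is no figure to reproduce. The check is direct arithmetic.

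Inputs:
- Divisor: visit-date difference + 1 (SAP 4.1.5.5).
- Nights enclosed by two morning visits k days apart: k (Protocol 5.2).
- Windows: SAP 4.5.3.3.6. V6 at D49, V7 at D56 and V8 at D63 come from Protocol 5.2.
- True night length: not in the documents. Assumed constant at 9 h, with a range of 8 to 10 h. The percentages do not depend on it.

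With every night recorded, reported mean = true mean × k/(k + 1), and shortfall = 1/(k + 1).

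| Window | k | k + 1 | Ratio | Shortfall | 9 h night reported as |
|---|---|---|---|---|---|
| Baseline D-28 to D0 (V0 start) | 28 | 29 | 0.966 | 3.4% | 8.69 h |
| Baseline D-14 to D0 (V1 start) | 14 | 15 | 0.933 | 6.7% | 8.40 h |
| DB4 as D21–D63 | 42 | 43 | 0.977 | 2.3% | 8.79 h |
| DB2 as D49–D63 | 14 | 15 | 0.933 | 6.7% | 8.40 h |
| DB4 if read as V4–V7 (D21–D56) | 35 | 36 | 0.972 | 2.8% | 8.75 h |
| DB2 if read as V6–V7 (D49–D56) | 7 | 8 | 0.875 | 12.5% | 7.88 h |

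False change with no real change in sleep, on the SAP 4.5.3.3.6 dates (8 to 10 h range in brackets):
- V0 start, baseline to D49–D63: 8.40 − 8.69 = −0.29 h (−0.26 to −0.32 h).
- V0 start, baseline to D21–D63: 8.79 − 8.69 = +0.10 h (+0.09 to +0.11 h).
- V1 start, baseline to D49–D63: 8.40 − 8.40 = 0.
- V1 start, baseline to D21–D63: 8.79 − 8.40 = +0.39 h (+0.35 to +0.43 h).

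Results are reported to 0.1 h (6 minutes), so most of these shifts would be visible.

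Internal check: take two adjacent 7-night periods of 9 h nights. Each gives 63/8 = 7.88 h, while the combined 14 nights give 126/15 = 8.40 h. A mean over a whole period cannot exceed the means of both its halves. The formula allows it because the shared visit date is counted in each half.

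Unrecorded nights: if 12 of 14 nights in D49–D63 are recorded at 9 h, the formula gives 12 × 9/15 = 7.2 h. Of the 1.8 h lost, 9 − 8.4 = 0.6 h comes from the extra day and 2 × 9/15 = 1.2 h from the two nights counted as zero.

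With recorded nights as the divisor, the complete-diary results are 252/28 = 126/14 = 378/42 = 9.0 h in every window.

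**The case against.** The strongest reply is that the SAP does not say whether a night belongs to its bedtime date or its wake date. The diary runs continuously and a new one is issued at V2 and at V7. If records are keyed by date, as the SAP's rule for several times on one date suggests, the evenings from D-28 to D0 inclusive give 29 entries over 29 days and baseline is unbiased. The same holds for V6–V7, with 8 evenings over 8 days. This is a fair point about an unstated boundary, but it does not rescue the formula. It relies on a night outside the visit interval that the SAP does not assign to the period. It also fails at D63: the blind-phase diary ends at V8, so no evening entry follows. D49–D63 would stay at 14/15 and D21–D63 at 42/43. With an unbiased baseline, the false change to D49–D63 would become 8.4 − 9.0 = −0.6 h, which is larger than under the natural reading.

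Two stronger readings are tempting and are not supported. First, a reader might take 12.5% as the headline, with a false loss of about 49 minutes (7.88 − 8.69 = −0.81 h). That needs DB2 to mean V6–V7, a label given only for the cataplexy rate in SAP 4.5.3.2.3. For night duration, SAP 4.5.3.3.6 gives D49–D63.

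Second, a reader might infer that the table will show spurious drug-induced sleep loss. The artefact has no single direction: it is negative, zero or positive depending on the window and the starting visit. The placebo column carries the same factor, no test or change-from-baseline variable is planned, and insomnia is captured through adverse event reporting (SAP 4.5.4.1).

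It is also true that night duration is exploratory and drives no decision. That limits the importance of the error but does not make the divisor right.

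**Conclusion.** The formula is wrong as written, with minor consequences. On the natural reading, in which the nights of a period are those between its first and last morning visits, a complete diary is understated by 3.4% at baseline from D-28 (6.7% from D-14), 2.3% over D21–D63 and 6.7% over D49–D63. It reaches 12.5% only if DB2 is V6–V7. For a constant 9 h night the false change runs from about −0.3 h to +0.4 h, depending on the window and on whether the patient started at V0 or V1. Unrecorded nights lower the mean further.

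Absolute hours and apparent within-arm changes are distorted. A between-arm difference within a window is shrunk by k/(k + 1), for example 14/15 over D49–D63, and does not change direction. This assumes equal windows, a similar V0/V1 mix and similar diary completeness in the two arms. The 9 h night is an assumption. The primary endpoint and the tested secondary endpoints do not use this night-duration formula, so no confirmatory conclusion is affected.

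**What to change.** - In SAP 4.1.5.5, compute mean night duration as the sum of night durations divided by the number of nights in the window with both bedtime and wake-time recorded.
- State which nights belong to each window, for example those starting on the evening of the first visit and ending on the morning of the last.
- Reconcile the DB2 and DB4 definitions: SAP 4.5.3.2.3 equates D49–D63 and D21–D63 with V6–V7 and V4–V7, while SAP 4.5.3.3.6 gives the dates alone. D56 to D63 is the placebo wash-out week, so the choice also decides whether off-drug nights are included.
- Report the number of recorded nights per patient and window beside the mean, so that thin diaries are visible.

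This needs a one-line change to the derivation and a sentence on windows. It needs no new data and no change to the design, and it costs nothing.

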## 4.1.5.6 Safety data

Adverse Event

## • Treatment Emergent Adverse Event

A Treatment Emergent Adverse Event (TEAE) corresponds to an Adverse Event (AE) that occurred on or after first dose of treatment up to 7 days post-last dose.

In case of partially/fully missing AE start date:

- Following imputation rules should be applied in order to determine whether the AE is treatment-emergent or not:
  - If only start day is missing, then it will be replaced by the minimum of (last day of the month, last treatment dose intake)
  - If both start day and month are missing then:
    - if year is equal to the year of the first treatment dose intake, then start date will be replaced by the first treatment dose intake

- if year is greater than the year of the first treatment dose intake and equal to the year of the last treatment dose intake, then start date will be replaced by the last treatment dose intake
- if year is greater than the year of the first treatment dose intake and smaller than the year of the last treatment dose intake, then start date will be replaced by 1-July
- $\circ~$  If start date if fully missing, then start date will be replaced by the date of the first treatment dose intake
- Emergence will be checked in accordance with the response to the question « Started before study drug intake ». If the response is "Yes" the AE can't be considered as emergent

# • Treatment Emergent Adverse Events related to study treatment

An event is considered to be related to the study treatment if the assessment of imputability is likely related or possibly related, or if the assessment is missing.

# **o** Non-Treatment Emergent Adverse Events (non-TEAEs)

Non-TEAEs are AEs that occurred prior to treatment.

## **o** Serious Adverse Events

By definition, a serious AE (SAE) is an AE that, at any time, fulfils one or more of the following criteria:

- results in death,
- is life threatening (patient at risk of death at the time of the event),
- requires in-subject hospitalisation or prolongation of existing hospitalisation,
- results in persistent or significant disability/incapacity,
- is a congenital anomaly/birth defect,
- is any medically important.

The seriousness of the event will be directly assessed by the investigator (specific variable within the AE database); therefore no derivation is needed.

## • Special Interest AEs

Special Interest AEs are AEs with the following MedDRA Preferred Terms (PTs):

# $\circ$ Treatment Emergent Adverse Events in the stable dose period

The stable dose is the treatment dose taken during the period V5 to V7. So TEAE in the stable dose are TEAE occurred between visit V5 (included) and the visit V7 (included)

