## 3.3 Study plan

## 3.3.1 Study duration

The expected duration of patient participation from the screening visit (V0) until the final blind visit (V8) will be 13 weeks, including:

- Baseline period without investigational treatments (from V0 to V2): 4 weeks,
- Low and medium dose titration phase (from V2, randomisation, to V3): 2 weeks,
- Individual dose adjustments (from V3 to V5): 2 weeks,
- Stable dose phase (from V5 to V7): 4 weeks,
- 1-week study drug wash out (placebo) after study drug discontinuation.

During the blind phase, the patient will be followed in an ambulatory way by 9 visits (8 visits during double blind period and 1 visit for the single blind period) on the site.

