# 4.1.5.3 Completers

- Completers the double blind period Patients who completed the study until the visit V7.
- Completers the blind period Patients who completed the study until the visit V8.

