# Safety Set (SAF):

All patients who receiving at least one treatment dose.

4 subgroups will be used in some analyses, according to:

- Age at baseline ([6-11], [12-18[)
- Sex
- BMI at baseline (underweight , normal, overweight and obese)
- Type of narcolepsy (Type 1 or Type 2)

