# 4.5.4 Safety data

All safety analyses will be performed by actual treatment group in the Safety Set.

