## 4.5.4.1 Adverse events

The Adverse events (AEs) were reported with the following information: Description, Visit number when AE was reported, Dose of study drug when AE occurred (10 mg, 20 mg, 40 mg, NA), Date of onset or worsening and end date or ongoing, Intensity (mild, moderate, severe), Frequency (once, intermittent and number and period, continuous, unknown), Action taken with studied drug (none, dose modification, temporary interruption, discontinued), Action taken with event (none, corrective treatment, additional exploration, hospitalization  $\leq$  24 hr, hospitalization > 24 hr), Serious adverse event (SAE) (yes, no), Outcome (recovered, recovered with sequelae, worsened, not yet recovered, death), Imputability (likely related, possibly related, unlikely related), Etiology (studied drug, concomitant treatment, associated disease, other, unknown)

Number of events, number and percentage of patients reporting at least one event, presented by primary system organ class (SOC) and preferred term (PT), over the period V2-V8, will be provided for:

- AE
- Serious AE,

- Treatment emergent AE (TEAE), Treatment emergent AE (TEAE) during the stable dose period, TEAE leading to IMP withdrawal, TEAE related to IMP, serious TEAE, severe TEAE, non-serious TEAE (EUDRACT), Treatment emergent fatal AE.
- Special Interest TEAE (SITEAE).

TEAE also will be described according to the intensity, dose in the stable dose period and outcome.

In case a same patient presented the same AE (i.e. same AE as defined according to SOC and PT) several times during the study, only one occurrence per patient will be reported, but the total number of events will be given.

In addition, only TEAEs with incidence >5% (i.e. % of patients with >5 % for a given PT in at least one treatment group) will be presented by SOC and PT in the SAF population.

A listing with all the individual AEs with the associated information will be provided.

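### The stable-dose TEAE percentage uses the whole Safety Set as denominator, so children who stopped before V5 count as event-free in a period they never entered

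*SAP*

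**What the plan says.** Four parts of the SAP together determine this table.

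- **Window.** SAP 4.1.5.6, on TEAEs in the stable dose period: "TEAE in the stable dose are TEAE occurred between visit V5 (included) and the visit V7 (included"). SAP 3.3.1 gives the length: "Stable dose phase (from V5 to V7): 4 weeks".
- **Statistic.** SAP 4.5.4.1 asks for "Number of events, number and percentage of patients reporting at least one event" and lists "Treatment emergent AE (TEAE) during the stable dose period" among the rows. It also describes TEAEs by the dose held in that period.
- **Population.** SAP 4.5.4: "All safety analyses will be performed by actual treatment group in the Safety Set". SAP 4.3 defines that set as "All patients who receiving at least one treatment dose".
- **Outer limit of any TEAE.** SAP 4.1.5.6 requires that the event "occurred on or after first dose of treatment up to 7 days post-last dose".

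The SAP defines no subset of patients who reached V5. The general percentage rule in SAP 4.1.2 takes only missing or unknown responses out of the denominator. In SAP Table 1, premature withdrawal has its own column, separate from V7, and takes place no more than 5 days after the last dose.

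**The concern.** The stable-dose table should tell a reader how well the maintained dose is tolerated. Its numerator can contain only children who were followed from V5, but its denominator contains everyone who took one tablet. A child who left in weeks 1 to 4 could not have contributed an event, yet is counted as not having had one. SAP 4.1.2 does not remove that child, because the absence of an adverse event record in the window is not a missing response.

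The by-dose rows have the same difficulty in a sharper form: a child who left before V5 has no stable dose and belongs to no dose group.

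The upper bound raises a second, smaller point. For a child who stops between V5 and V7 the V7 date does not exist, and the definition names no replacement. The events affected are those around discontinuation, which a tolerability table should handle in a stated way.

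**Working it through.** The plan gives no figure to reproduce, so the check is the dilution arithmetic and then a reading of the window.

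**1. Dilution.** In one arm let N be the Safety Set size, L the number who left before V5, and E the number with at least one stable-dose TEAE. The incidence among children reaching V5 is p = E/(N − L). Following the SAP, the table shows

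E/N = p × (N − L)/N = p × (1 − d), with d = L/N.

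Both p and d are assumptions.

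| d (assumed) | Shown if p = 20% | Shown if p = 30% |
|---|---|---|
| 5% | 19.0% | 28.5% |
| 10% | 18.0% | 27.0% |
| 15% | 17.0% | 25.5% |
| 20% | 16.0% | 24.0% |

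The understatement is 1.0 to 4.0 points at p = 20% and 1.5 to 6.0 points at p = 30%.

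The nearest figure in the documents is in Protocol 7.7.2: 25 of 27 randomised patients had values at V6 and V7, so 2/27 = 7.4% did not. This covers loss at any time, is not split by arm, and is not a rate of loss before V5. Used only as a reference value, it gives 30% × 25/27 = 27.8%.

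**2. Comparison between arms.** If p is the same in both arms, the spurious difference (pitolisant minus placebo) is p × (d for placebo − d for pitolisant). The illustration uses the planned 72 and 36 patients (SAP 4.2).

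- Equal proportional loss, 4 of 72 and 2 of 36: 30% × 68/72 = 28.3% and 30% × 34/36 = 28.3%. The difference is zero.
- Unequal loss, assumed 11 of 72 and 2 of 36: 30% × 61/72 = 25.4% and 30% × 34/36 = 28.3%. The difference is −2.9 points. At p = 20% the figures are 16.9% and 18.9%, a difference of −1.9 points.

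The arm with more early loss looks better tolerated.

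**3. End of the window.** For a child who stops after V5 and has no V7 visit, three end dates fit the text: the last dose, the withdrawal visit (up to 5 days later), and the TEAE limit (7 days later). A program that tests onset against a V7 date that is missing could also drop the events. The SAP does give a fallback for another variable: for the MWT, SAP 4.5.3.2.4 accepts the last on-study visit in place of V7. The stable-dose definition has none.

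**The case against.** **The denominator is inferred.** The SAP does not state it for this row. It follows from the blanket Safety Set rule, and SAP sections 5 and 6 refer to mock tables in a separate file that is not part of the supplied documents. Those shells may show a different N. This stands as a caveat, but the rule as written has no exception.

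**The window is not open-ended.** A reader might infer that events in a child who stops after V5 have no end date, or that they are necessarily excluded. Neither follows. Any TEAE is already limited to 7 days after the last dose, and the text does not call for exclusion. What remains is an ambiguity.

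**No event disappears from the report.** A reader might infer that the adverse events that ended treatment would be lost. SAP 4.5.4.1 also provides tables over V2 to V8, including all TEAEs and TEAEs leading to withdrawal of study drug, and a listing of every adverse event. Only the stable-dose rows are affected.

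**Starting at V5 is consistent.** The dose may still be lowered at V5, so a reader might think the window should open later. The Protocol synopsis starts the 4-week stable period at V5, and Protocol 5.1 and SAP 3.3.1 both run it from V5 to V7. The SAP follows the protocol here.

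**An at-risk denominator has its own selection.** It conditions on completing titration, which treatment can affect. If one arm loses its least tolerant children early, the restricted percentage can flatter that arm too. This stands. It is a reason to show the number lost before V5 beside the percentage, not a reason to count those children as event-free.

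**Unequal early loss is assumed.** The documents contain no such rates, so they do not support a claim that pitolisant will look falsely well tolerated.

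**Conclusion.** The point holds in a limited form. Applied as written, the SAP understates the incidence of stable-dose TEAEs among children who reached V5 by the factor (1 − d). The dilution itself follows from the definitions; its size rests on assumed p and d. The comparison between arms is distorted only if early loss differs. The end of the window is undefined for children who stop after V5 without a V7 visit, so those counts depend on a programming choice.

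The consequence is modest. The table is descriptive, no test depends on it, and the overall tables remain intact. The change is still worth making before database lock, because a table on the maintained dose should be based on children who reached that period, and the correction is almost free.

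**What to change.** In SAP 4.5.4.1, state that for the stable-dose TEAE table the denominator is the Safety Set patients still on double-blind treatment at V5, and that for the by-dose rows it is the number on each stable dose. Count events only in those patients. Show these numbers per arm, together with the number who left before V5.

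In SAP 4.1.5.6, state that the window opens at V5, as now, and closes at V7 or, for a child who stops after V5 without a V7 visit, at the existing TEAE limit of 7 days after the last dose. Closing it at the last intake instead would not do: it would drop events that start just after stopping, which the SAP already counts as TEAEs.

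Leave the V2 to V8 tables on the full Safety Set, and align the mock tables.

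The cost is about one sentence in each section and no new data. The percentages rise slightly and describe only children who completed titration, which the table should say.
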